Comparison of home-based palliative care delivered by community health workers versus usual care: research protocol for a pilot randomized controlled trial

Study Protocol

NCT04972630

April 4, 2019

A. SIGNIFICANCE

A.1. Global Need for Evidence-Based Palliative Care Models. Annually over 40 million people worldwide could benefit from palliative care to control pain and other symptoms, but only about 10% receive these services. Palliative care can improve the quality of life (QOL) of patients and their families facing life-threatening illness through pain and symptom management. Medical conditions that frequently require palliative care include cancer, HIV/AIDS, and congestive heart failure. In 2014, the World Health Organization (WHO) published the first Atlas of Palliative Care, documenting the global distribution of need and availability of palliative care. While palliative care primarily exists in North America, Europe and Australia, approximately 80% of patients who need these services live in limited resource countries. Palliative care research has almost entirely been conducted in high resource countries. Palliative care can reduce pain⁴⁻⁵ and symptom burden,^{2,6} increase QOL,⁷⁻⁸ satisfaction with care,⁹⁻¹¹ and the likelihood of dying in one's own home.² At a health-system level, palliative care can reduce hospitalizations, 10-12 ER visits, 13 and healthcare costs. 2,14 Unfortunately, dissemination and implementation of palliative care to limited resource settings has been extremely limited 15-16

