- **C.3. Guiding Framework.** As shown in Table 2, the RE-AIM framework guided our evaluation plan to measure the reach, effectiveness, adoption, implementation and maintenance of the home-based palliative care intervention (Pal-Care).²²
- **C.4. Study Overview.** This pragmatic clinical trial (PCT) will examine how the Palliative Care Toolkit, which provides comprehensive evidence-based materials for delivering palliative care, can be adapted for use by CHWs working with a cancer center to deliver home-based palliative care for rural patients. The study will compare an intervention group of patients who will receive home-based palliative services from

CHWs vs. a control group of patients who will receive cancer-center based palliative services. Diverse data sources will be used to evaluate the intervention within the REAIM Framework. These include patient care logs completed by CHWs, longitudinal surveys of intervention and control group patients, chart reviews of medical record and billing data and post-intervention interviews with the clinical team, CHWs and patients/caregivers.

- **C.4. Study Setting and Partners.** This research is a collaboration between the Medical University of South Carolina (MUSC) and the Tata Medical Center (TMC), Kolkata, India. The study will be conducted at the TMC located in Kolkata, India. TMC is a premier regional cancer center in Eastern India, which has approval by the Indian government to conduct research, a well-established research infrastructure, including a variety of active studies, and its own institutional review board.

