- Participant Recruitment and Informed Consent: All study recruitment and C.8.2. consent activities will be conducted onsite at the TMC. Using the NCI screening log, the research coordinator will systematically screen all TMC patients who require palliative care for study eligibility. Inclusion criteria: age 18+, any cancer type of which the PI feels have a cluster of symptoms that can be managed at home and not require hospitalization, late stage cancer, an ECOG status of 0-3, residence in 24 Parganas regions, physician documentation in paper medical record that patient is to receive palliative care, and patient willingness to participate in data collection. These broad eligibility criteria will be used, as the study will evaluate the intervention under real world conditions. For patients who meet eligibility criteria, the research coordinator will introduce the study and assess interest in participation. Interested patients will be referred to their palliative oncologist to answer questions about the study and complete informed consent. Next, the palliative care physician will randomly assign patients to intervention or control group. For each patient screened, the research coordinator will document if patient was offered, consented to and dropped out of study, and reasons for screen failure and drop out. This will enable assessment of feasibility of our recruitment plan, plus generalizability of study participants to the 24 Parganas Regions. Participants will receive \$15 for study participation upon study enrollment and at each of three follow-up survey intervals towards their travel expenses.

Table 2: Evaluation Measures Organized within the REAIM Framework			
Outcome	Measures	Collection/Time Points	
Aim 1: Evaluation of Intervention Implementation			
CHW Training/ Orientation	Attendance rates for program orientation, trainings and meetings among CHWs and clinical team; Pre/post-test change in CHW's palliative care knowledge and perceptions; CHW's skills performance and perceptions of training content and format post-training	Minutes from home-based palliative program meetings TMC Co-ls will administer	
		survey pre-post training & skills checklist post-training	
CHW Role	Frequency of patient visits; assessment of patient problems (e.g. pain, transportation, depression); CHW actions (education, scheduling appt., obtaining morphine); problem resolution (pain control); frequency of debriefings with clinicians	Review of toolkit log data	

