Study Recruitment	Number, % and characteristics of eligible patients who are offered study participation, consent and complete/drop-out; reasons for screen fails and dropout	TMC research coordinator will complete recruitment and enrollment logs	

Stakeholder Perceptions	Perceptions of Pal-Care intervention implementation/feasibility among clinical team members, CHWs and patients/caregivers, with comparisons by stakeholder type	[name] will conduct qualitative interviews	
Fidelity to Study Protocol	Participant recruitment per inclusion criteria; data collection per protocol (% completion of patient surveys and each type of toolkit form), regular meetings with research team/sites with high attendance; timely reporting of adverse events	Patient record reviews, review of completed surveys and toolkit forms, meeting minutes	
Aim 2: Evaluation of Intervention Effectiveness			
Patient Outcomes	Patient surveys will be conducted with intervention/control groups to assess: palliative needs via African Palliative Outcomes Scale; ²⁴ QOL via WHO QOL Scale; ²⁵⁻²⁷ cancer symptoms via Edmondton Symptom Scale ²⁶⁻²⁹ and patient care experience via FAM-Care Scale. ³⁰⁻³¹	TMC research coordinator will administer surveys by phone after baseline study visit and at 1 and 3 months	
	Palliative care toolkit forms ³ filled out by CHWs measure outcomes for intervention group: use of pain, anti-emetics and laxative medications; performance status; survival days in palliative service; location of death.	Review of toolkit form data	

C.8.3. Intervention Group: Intervention group participants will receive the Pal-Care intervention that we developed, which is based upon: 1) the Palliative Care Toolkit materials and 2) key adaptations we identified in our prior stakeholder interviews. The intervention will be delivered over a 6-month period. For patients in the intervention, the research coordinator will set up an appointment for the patient and their caregiver to meet with their CHW and clinical team, including the oncologist, social worker and nurse. At this meeting, a baseline health and needs assessment will be conducted and an individualized care plan will be created.

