- C.8.5. Post-Intervention Transition of Care: After study participation, all patients (or family on their behalf) may continue to receive palliative care at the cancer center for as long as needed. As the cancer center will hire CHWs for the grant period, intervention group patients may continue receiving services from their CHW until the study ends (i.e. past the final 6-month assessment). Once the study ends and CHWs are no longer paid by the grant, intervention group patients may transition to cancer-center based care or continue receiving supportive services from their CHW for a small fee per visit. Fees traditionally charged by CHWs for home visits are very reasonable and we will work with them to establish a standard fee structure for palliative visits.
- C.9. Data Collection, Measures and Management: Table 2 displays study outcomes, strategies and time points for data collection, with mapping to RE-AIM Framework domains. The three primary data sources for this study include WHO Toolkit logs completed by CHWs, longitudinal surveys with intervention and control group patients/caregivers, and post-intervention stakeholder interviews. Supplemental data sources include meeting minutes, training evaluations, study recruitment logs, and chart reviews of cancer center medical record/billing data. Based on our pilot, cancer center stakeholders prefer using hard copy patient care logs and assessment tools. Thus, data will be collected via pen and paper, with data transfer into a password protected webbased data system, Research Electronic Data Capture (REDCap) (§ Facilities and Other Resources).

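### No harm is counted by arm: adverse events appear only as a reporting-timeliness item, and death outcomes are listed for the intervention arm alone

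*Protocol*

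**What the plan says.** **Adverse events.** The one mention is in Protocol Table 2 (Aim 1, Fidelity to Study Protocol): "timely reporting of adverse events". The sources for that row are "Patient record reviews, review of completed surveys and toolkit forms, meeting minutes". Neither document gives an event definition, a collection form, a time window or a count by arm.

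**Event-type outcomes.** Under Aim 2, Table 2 lists "survival days in palliative service; location of death". These belong to the toolkit forms, which are "filled out by CHWs measure outcomes for intervention group". No control counterpart is named.

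**Sources that could reach both arms.** C.4 plans "longitudinal surveys of intervention and control group patients". The four survey instruments cover palliative needs, quality of life, symptoms and experience of care, and no event question is named. C.9 lists "chart reviews of cancer center medical record/billing data" as a supplemental source, without naming variables or arms, and no Table 2 outcome uses it.

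**Analysis.** C.12 and the SAP give general methods for continuous and categorical variables and name no harm.

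**Task shift.** Under C.8.3, CHWs give medication, wound and catheter care at home and bring morphine to patients.

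**The concern.** The trial moves hands-on care to workers for whom C.13 names lack of palliative experience as one of two main challenges. A pilot of such a model would normally hand its successor a simple table of what went wrong, and how often, in each arm. This plan would yield a timeliness figure and, for the intervention arm only, survival days and place of death recorded by the people delivering the care.

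Admissions and emergency visits are natural events to count. Eligibility requires symptoms that "can be managed at home and not require hospitalization", and A.1 states that "palliative care can reduce hospitalizations" and emergency visits. Place and date of death, and admissions outside the Tata Medical Center (TMC), are hard to recover in controls afterwards if nobody asks at the time. So this is a gap in data collection as well as in reporting.

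**Working it through.** **1. Which planned source counts a harm, and in which arm?**

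| Source (place) | Arms | Harm counted? |
|---|---|---|
| Fidelity row (Table 2) | not stated | No; timeliness only |
| Toolkit forms (Table 2, C.9.2) | intervention only | Survival days, place of death |
| Coordinator surveys (Table 2, C.9.1) | both | No event question named |
| Chart and billing review (C.4, C.9) | not stated | No variable named |
| Drop-out log (C.8.2, Table 2) | all patients screened | Reasons only; may show a death indirectly |
| C.12 and SAP | n/a | No harm named |

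No row gives a harm count in both arms.

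**2. The plan's own precision figure.** Inputs from C.11 and the SAP: 45 per arm, SD 2.5 to 5.0, 95% CI. Half-width = critical value × SD × √(2/45), with √(2/45) = 0.2108.
- z = 1.96: 1.96 × 2.5 × 0.2108 = 1.03; 1.96 × 5.0 × 0.2108 = 2.07.
- t on 88 df: 1.05 and 2.09.

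The stated ±1.0 to ±2.1 is reproduced. It covers change scores only; no precision is given for any harm.

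**3. What by-arm counts could deliver at 45 per arm.** The documents give no harm rates, so the rates p below are assumptions shown as a range.
- Upper bound after 0 events in 45: 1 − 0.05^(1/45) = 6.4% one-sided; 1 − 0.025^(1/45) = 7.9% two-sided.
- Chance of at least one event in an arm, 1 − (1 − p)^45: 60% at p = 2%, 90% at 5%, 99% at 10%.
- Approximate 95% half-width for the risk difference with equal rates, 1.96 × √(2p(1 − p)/45): ±9.0 points at 5%, ±12.4 at 10%, ±16.5 at 20%, ±18.9 at 30%.
- Power for 10% versus 20% (normal approximation, two-sided 5%): Φ[(0.10 − 1.96 × √(2 × 0.15 × 0.85/45)) / √((0.09 + 0.16)/45)] = Φ[(0.10 − 0.1476)/0.0745] = 26%.

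Counts would probably reveal events that are not rare and give rough rates for planning. They could not settle a comparison.

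**4. Does the follow-up schedule support common collection?** C.9.1 sets surveys at baseline and 1, 3 and 6 months, with follow-up at home. C.8.2 counts three follow-ups, and C.8.5 refers to a final 6-month assessment. Table 2 lists follow-up only at 1 and 3 months, by phone. If Table 2 governed, questions added to the surveys would miss months 3 to 6.

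**The case against.** The best reply is that this is a feasibility pilot, that 45 per arm cannot establish safety, and that much is already covered. The symptom and needs scales run in both arms and can show deterioration. Drop-out reasons are logged. C.12 and the SAP already provide frequencies, chi-square or Fisher tests and 95% CIs for categorical variables. The SAP takes its outcome list from a Results section not reproduced there, and the protocol cites an appendix, so a safety plan may exist elsewhere.

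Part of this stands. The analysis method is present; what is missing is a named variable and comparable data. A separate safety plan would lower the concern, but neither document refers to one. The scales and the drop-out log do not count admissions, emergency visits or deaths. C.11 says pilots test measurement protocols, and harm measurement is one of these.

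Four stronger readings may tempt a reader, and the documents do not support them.
- *Controls are barely observed while CHWs visit weekly.* C.8.4 has controls collecting medication weekly, in person or by proxy, and gives them a 24/7 hotline. The sources differ in kind, but a contrast in contact numbers is not established.
- *Intervention patients' TMC records will be thinner because CHWs collect their morphine.* C.8.3 also has CHWs debriefing the cancer center team weekly, which could make those records fuller.
- *Unequal capture will produce a spurious difference of a given size.* The documents give no event or capture rates, and the plan makes no by-arm event comparison.
- *Admissions directly test the home-management premise.* The eligibility judgement applies to both arms, and the A.1 statement concerns palliative care generally, which both arms receive. CHWs are also meant to help patients reach their oncologist, so more attendances could reflect good detection.

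**Conclusion.** The gap is real. Adverse events are measured only for timeliness of reporting, no harm is counted by arm, and even deaths have no planned control comparison. As written, the pilot cannot describe harms by arm.

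A reader might go further and infer that counting harms would show whether CHW-delivered care is safe. It would not: zero events in 45 still allows about 6.4% one-sided (7.9% two-sided), and at an assumed 10% rate the risk difference is known only to about ±12 points. The gain is descriptive input for the larger study named in C.14. I rate this as a cheap improvement that should be made. The conclusion assumes that no safety plan outside these two documents already provides by-arm collection, and the precision figures assume full follow-up of 45 per arm.

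**What to change.** **Outcome.** Add to Table 2 and the SAP a descriptive by-arm safety outcome for all randomized patients: death (date and place), unplanned hospital admission and emergency attendance, including care outside TMC.

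**Collection, the same in both arms.**
- Two or three fixed questions at each coordinator follow-up at 1, 3 and 6 months, answered by the caregiver if the patient has died or cannot respond. Table 2 must be reconciled with C.9.1 on the 6-month survey and on phone versus home administration.
- The planned TMC chart and billing review, stated to cover both arms over the same 6-month window. The survey questions are needed as well, because TMC records would miss care given elsewhere.

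**Reporting.** Give the number of patients with each event by arm with exact 95% CIs, and deaths separately, since death prevents later admissions. State that these are input to the larger trial and not evidence of safety. List adverse events that the site judges related, and events known only from CHW forms, outside the arm comparison. C.8 blinds only the US investigators and statisticians, so the site's judgement is unblinded, and the CHW forms exist in one arm only. Keep timeliness as a fidelity item.

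**Cost.** Slightly longer surveys for very ill patients, one more chart-review field and one SAP table. No extra visits or staff are needed.

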- C.9.1. Patient Surveys. Surveys will be conducted with study participants at study entry (baseline) and at 1, 3 and 6 months to assess patient outcomes. The TMC research coordinator, a native Bengali speaker, will administer the baseline survey after informed consent and will travel to patient homes to administer follow up surveys. As patients have low literacy and are very sick, we selected brief instruments that use simple language and response options. Multi-dimensional palliative care outcomes will be assessed with the 10-item African Palliative Outcomes Scale that measures physical and psychological symptoms; spiritual, practical and emotional concerns; and psychosocial needs of patient/family on a 5-point likert scale.²⁴ QOL will be assessed with the 26-item WHO QOL Scale, 25-27 that assesses physical health, psychological health, social relationships and environment on a 5-point likert scale. Cancer symptoms will be assessed with the 9-item Edmondton Symptom Scale. 29-30 Experience with care will be assessed with the 16-item FamCare Patient Scale³⁰⁻³¹ measured on a 5-point likert scale. These instruments have established validity and reliability and have been used in palliative populations and limited resource settings including India, but have not been translated into Bengali. Surveys will be translated using standard translation/back translation to ensure accurate translation.
- C.9.2. Palliative Care Toolkit Forms. Toolkit forms^{3,33} include: 1) a record of patients in CHW's caseload; 2) a home visit record to track services, including main problems, care provided and visit notes; 3) a patient-held home care record to longitudinally document visits to patient, their condition and main problems, care provided and notes;

- 4) a patient-held drug chart to record name and purpose of each drug, dose and form of medication, and when each dose should be taken; 5) a patient held morphine record to document form, strength, and administration dates/times; 6) a referral form for services and resources; and 7) a monthly report to document number of patients under care, their diagnoses and contacts, new referrals, and end of care outcomes.

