- **C.12. Analysis Plan:** Table 2 describes measures to be collected to evaluate study aims. Data will be analyzed in SAS.³⁶ For aim 1, implementation mesures will be reported as means, standard deviations, medians, range, frequencies and proportions as appropriate. When appropriate, outcomes will be compared between intervention and control groups using t-tests and chi-square tests (or equivalent nonparametric tests) as appropriate. For primary analyses for aim 2 the intent-to-treat (ITT) sample will be used comprising all randomized patients. Descriptive statistics will be calculated for all variables. For continuous variables we will report means, standard deviation, medians and ranges. We will compare between group differences for continuous variables using either t-test for variables that are normally distributed or can be log-transformed or a Wilcoxon rank sum test for variables if normality cannot be approximated. For categorical variables, we will report frequencies, percentages and compare between group values with Chi Square or Fisher exact test. 95% CIs will be

reported. In exploratory analysis to obtain variance estimates of effectiveness outcomes and the covariance structure of the longitudinal scores, generalized linear mixed models (GLMM) will be used to compare the two groups (intervention vs. control group) with intervention group as the primary independent variable and pain as the dependent variable. GLMM can account for clustering of measurements within CHW and within patients as well as accommodate missing data. Group (intervention vs. control group) will be a fixed effect; demographics (age, gender, distance from cancer center); and clinical (time since diagnosis, cancer type, baseline pain) variables will be adjusted for, along with a CHW variable accounting for cluster effects among patients by CHW. We will estimate the difference (via 95% CI) in average slopes between intervention and control groups and evaluate linearity of trajectories as input to inform a future trial. Further, dropout rate will be examined. If over 10% of data are missing, we will adjust data collection intervals in a future trial.

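### The survival-days outcome has no defined window and no censoring rule, so its planned mean counts living patients' time as complete

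*Protocol*

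**What the plan says.** Protocol Table 2, under Aim 2 patient outcomes, states that toolkit forms "filled out by CHWs measure outcomes for intervention group". The items include "performance status; survival days in palliative service; location of death". No start date, end date or handling of patients still alive is attached to the day count, there or elsewhere.

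Two passages bear on how long a patient can be in service:

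- C.8.3: "The intervention will be delivered over a 6-month period".
- C.8.5: "intervention group patients may continue receiving services from their CHW until the study ends (i.e. past the final 6-month assessment"). After the study, "intervention group patients may transition to cancer-center based care or continue receiving supportive services from their CHW for a small fee per visit".

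On records, C.9.2 lists among the toolkit forms "a monthly report to document number of patients under care, their diagnoses and contacts, new referrals, and end of care outcomes". No analysis rule goes with it.

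On analysis, C.12 says "Descriptive statistics will be calculated for all variables" and "For continuous variables we will report means, standard deviation, medians and ranges". The SAP repeats both sentences. It adds that measures will also be broken down by age, gender, cancer type and CHW caseload. Neither document mentions censoring, Kaplan-Meier or another time-to-event summary for this outcome. The mixed model does not cover it, because its dependent variable is pain.

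**The concern.** Time to death needs three things fixed before it can be summarised: when counting starts, when it stops, and what is done with patients who have not died by then. Here all three are open. A patient alive when counting stops contributes a number of days that is only a lower bound on survival, and the general rule for continuous variables enters that number into a mean as though it were complete.

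The open window adds a second problem, but only on one reading. If the count follows CHW service to study end, an early enrolee can accrue more days than a late one with the same survival. The SAP's breakdowns by cancer type and CHW caseload could then show differences that reflect enrolment timing alone. If the count stops at 6 months for everyone, this second problem does not arise.

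At stake is whether the pilot's survival summary can be interpreted. Two analysts following the text could report quite different figures from the same patients.

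**Working it through.** **The plan's own figure.** The only computed figure in the documents is the precision statement in C.11 and the SAP. With 45 per arm, half-width = 1.96 × SD × √(1/45 + 1/45):

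- SD 2.5 gives 1.03 and SD 5.0 gives 2.07.
- With the t distribution on 88 df, the values are 1.05 and 2.09.

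Both versions round to the stated ±1.0 and ±2.1. The statement concerns change scores and has no bearing on survival days.

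**Inputs for the illustration.** The documents give no survival figures, accrual period or study duration. The following are assumptions:

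- Survival T is exponential with median m months, so its mean is μ = m / ln 2.
- One month is 30.4 days.
- The counting window C is either 6 months for everyone, or spread evenly over 6 to 18 months by enrolment date.
- Every patient is followed until death or the end of the window.

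**Formula.** The expected mean of the recorded days, min(T, C), for a fixed window is μ × (1 − exp(−C/μ)). The bracket is the probability of dying within the window. Under exponential survival, therefore, the relative shortfall of the mean equals the proportion still alive when counting stops.

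**Median survival 6 months.** μ = 6 / 0.693 = 8.66 months = 263 days.

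- 6-month window: 263 × (1 − 0.5) = 132 days.
- 12-month window: 263 × (1 − 0.25) = 197 days.
- 18-month window: 263 × (1 − 0.125) = 230 days.
- Windows spread over 6 to 18 months: proportion alive = (8.66/12) × (0.5 − 0.125) = 0.27, so the mean is 263 × 0.73 = 192 days. Simulation with 1,000,000 draws also gives 192.

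**Sensitivity to the assumed median** (days; spread-window values are from the simulation):

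| Assumed median | True mean | Mean, 6-month window | Mean, spread windows | Alive at end of count (6-month / spread) | True median | Median, spread windows |
|---|---|---|---|---|---|---|
| 3 months | 132 | 99 | 120 | 25% / 8% | 91 | 91 |
| 6 months | 263 | 132 | 192 | 50% / 27% | 182 | 182 |
| 9 months | 395 | 146 | 232 | 63% / 41% | 274 | 225 |
| 12 months | 526 | 154 | 258 | 71% / 51% | 365 | 252 |

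The median is sound when it falls at or before the shortest window, and too low when it falls later.

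**Deaths only.** If the analyst instead averaged only patients who died, the 6-month-median case would give 81 days (6-month window) or 143 days (spread windows). The text does not rule this out.

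**A limit on the criticism.** With a common 6-month window and complete follow-up, the plain average of 132 days is exactly the restricted mean to 6 months. It is then a valid quantity if labelled as such. It stops being one if it is reported as mean survival, or if some living patients are lost before 6 months and their shorter counts are averaged in.

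**The case against.** The strongest objection is that no passage says the day count ends at study end. C.8.5 concerns the transition after participation and says only that patients may keep receiving CHW service. It does not say that outcome data continue to be collected. C.8.3 supports a common 6-month window equally well. This objection stands. A reader might infer that the figure necessarily depends on enrolment date, and cite 132 days for the last patient enrolled against 230 for the first. The documents do not establish that. The arithmetic is right under the assumptions, but it contrasts two extreme patients on one of two readings and is not the error in a reported figure. Nor is staggered follow-up itself a fault, since Kaplan-Meier handles administrative censoring.

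A reader might also infer that the reported figure is not survival at all. That is too strong. The median is reported too and can be correct, and the count is complete if every patient dies under observation. At an assumed 3-month median with spread windows, the mean is only about 9% low (120 against 132). The label can also be read as time in service, which is a legitimate utilisation measure.

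Two further inferences fail:

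- The t-test and Wilcoxon provisions do no harm here, because Table 2 collects the item in one arm only.
- Distortion of the location-of-death percentages is not shown. It would need the longer window and place of death that varies with survival time, and the documents address neither.

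Finally, this is a feasibility pilot, and survival is not among the outcomes given a precision figure. That limits the consequence.

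The missing censoring rule survives all of this. Under either window, the plan as written treats living patients' time as finished.

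**Conclusion.** The concern holds in a limited form. The window is undefined, and the stated summary rule takes no account of patients alive at last observation. The mean therefore understates survival unless every patient dies under observation. Dependence on enrolment date is conditional on counting to study end.

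Under the assumed survival medians of 3 to 12 months, the mean would be 25% to 71% low with a 6-month window and about 9% to 51% low with windows spread over 6 to 18 months. These sizes rest wholly on assumed survival and accrual and say nothing about what this trial will observe.

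The outcome is descriptive and confined to the intervention arm. No between-group comparison is biased and the sample size is untouched. It is worth correcting because the correction is cheap and the figure is otherwise open to several incompatible computations.

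**What to change.** In Table 2, C.12 and the SAP:

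- Define the outcome as days from randomisation to death. Censor patients who are alive at one stated cut-off (the 6-month assessment or study end), or at the last known alive date if earlier.
- Replace mean and SD for this item with Kaplan-Meier estimates, or with restricted mean days to 6 months labelled as such. Kaplan-Meier recovers the survival curve only up to the longest follow-up, and only if censoring is administrative. Patients who leave service alive for other reasons should therefore be counted and described.
- Report location of death over the same window, with still alive as its own category.
- List total days in CHW service separately, as a measure of utilisation.

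The cost is wording and a little analysis work. The data must hold a date of death or last known alive date for each patient. The monthly report in C.9.2 already records how care ended, but the documents do not say that it records dates, so this should be checked. If the 6-month horizon is chosen, later deaths drop out of the main summary.
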